7.2.2 Other Safety Assessments

Injection site reactions

Injection site reactions (*redness, swelling, tenderness/pain, and other* as judged by the investigator) and axillary lymphadenopathy, defined as Lowest Level Term Lymphadenopathy axillary, on the same day as a vaccination as well as all injection site reactions after latest vaccination will be presented as follows:

- The number and percentage of participants as well as number of events will be summarised by treatment group and by vaccination (starting after 1st and after 2nd vaccination).
- The maximum size of the redness and swelling on the same day as a vaccination and in total within 7 days after latest vaccination will be summarised by treatment group and by vaccination.
- Injection site reactions will be listed including type and maximum diameter in mm and onset relative to the two vaccinations.

Temperature reactions (pyrexia)

Temperature reactions are events with PT *Pyrexia*. The maximum temperature could be recorded in the CRF. The maximum temperatures will be summarised by treatment group and vaccination (1st and 2nd). A listing will be made for all systemic reactions including pyrexia with maximum temperature if available.

Vital Signs

Vital signs (systolic and diastolic blood pressure, pulse, and axillary temperature) will be measured at each visit from 2nd screening visit (Visit 2) to Visit 6 (Day 70), and at ET visit. At Visits 3 and 5, the measurements are taken both pre-vaccination and one-hour post-vaccination.

Vital signs will be summarised by visit, including change from pre-vaccination to post-vaccination within Visit 3 and 5, respectively. For each visit it will be flagged whether there are any abnormal clinically significant vital signs. All information will be listed.

Height, Weight, and BMI

Weight is measured at all onsite visits from 1st screening visit (Visit 1) and onwards. Weight will be summarised by treatment and visit, including change from baseline, (Visit 3, Day 0) to subsequent visits. Height is measured at 1st screening visit (Visit 1) and BMI will be calculated for that visit. Height and BMI will be summarised by treatment, see section 4.3. All information will be listed. Furthermore, a box plot will present weight by visit and treatment.

Physical Examination

A complete physical examination is performed at 2nd screening visit (Visit 2). Symptom directed physical examination is performed at the two vaccination visits, Visit 3 and Visit 5. Each body system

of the physical examination will be evaluated as normal or abnormal, and if abnormal clinically significant or not. Abnormal clinically significant findings will be listed by participants.

TB symptoms

From visit 4 (Day 14) and throughout the trial TB symptom screen will be performed. TB signs or symptoms will be summarised by symptom, treatment, and visit, including telephone contact (TC) visits. All signs or symptoms that occur will be listed. If a symptom screen was not performed, this will be in the listing including the reason why symptom screen was not performed.

Pregnancy test

Pregnancies and pregnancy outcomes will be listed.

7.2.3 Laboratory Safety Data

Laboratory safety (haematology, biochemistry, and urine analysis parameters) are measured at 2nd screening visit (Visit 2) for all participants, and at Visit 4 (day 14), Visit 6 (day 70) and at ET visit for participants in the safety cohort. Laboratory safety will also be measured at the ET visit if the visit occurs within 14 days after investigational product administration. Additional laboratory tests may be performed if deemed necessary by the investigator for evaluation of an AE.

The following safety laboratory parameters are measured and will be presented using SI units:

- Serum chemistry: AST ($\mu\text{Kat/L}$), ALT ($\mu\text{Kat/L}$), ALP ($\mu\text{Kat/L}$), GGT ($\mu\text{Kat/L}$), total bilirubin ($\mu\text{mol/L}$), creatinine ($\mu\text{mol/L}$).
- Hematology: haemoglobin (g/L), haematocrit (L/L), leukocytes ($10^9/\text{L}$), lymphocytes ($10^9/\text{L}$), monocytes ($10^9/\text{L}$), neutrophils ($10^9/\text{L}$), basophils ($10^9/\text{L}$), eosinophils ($10^9/\text{L}$), and platelets ($10^9/\text{L}$).
- Urine analysis: urine protein, glucose, leukocytes, and erythrocytes (microscopy if positive by dipstick).

Laboratory safety biochemistry and haematology will be presented by visit and treatment using summary tables and boxplots. Urinalysis will be summarised by visit and treatment using the categories as collected in the eCRF.

All safety laboratory data will be listed by participant, including unscheduled measurements. Values outside normal ranges will be flagged and presented in a separate listing including normal ranges.

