2.2 Design

This is a phase 2, double-blind, randomized (1:1), placebo-controlled study with 2 parallel groups:

- H56:IC31 (investigational vaccine)
- Placebo

900 HIV-negative adults with a diagnosis of drug-susceptible pulmonary TB are planned to be included, recruited from TB clinics with established relationships to the study sites see Table 2-1.

5 study sites in South Africa: 2 sites from the [REDACTED] and three in Cape Town at [REDACTED] and [REDACTED].

1 study site in Tanzania (TZ): 1 site at [REDACTED].

Table 2-1 Treatment Groups and Number of Participants

Number of Doses	Treatment Assignment N (planned)		Total N (planned)
	H56:IC31 5 µg H56/ 500 nmol IC31	Placebo	
All randomized participants in study 2 x 0.5 mL (Days 0, 56) intramuscularly in deltoid	450	450	900
First 150 randomized participants across all sites Safety cohort subgroup	75	75	150
First 100 randomized participants [REDACTED] sites only Immunogenicity cohort subgroup and control cohort	50	50	100

For the summary schedule of participant evaluations, see Table 3.1. For a flowchart showing the study design, see Figure 2-1.

Screening Visits 1 and 2

The 1st screening visit (V1) must be conducted ≤ 7 days after the start date of the TB treatment. The 2nd screening visit (V2) must be conducted ≥ 5 months (22 weeks) after the start date of TB treatment. The end of TB treatment is expected to be 6 months (24 weeks) after the start of TB treatment and may not be extended beyond 28 weeks. At V1 informed consent will be obtained and inclusion and exclusion criteria (applicable for V1) will be assessed, by review of medical history. Demographics, height, weight, smoking history, Xpert MTB/RIF result or AFB smear positive result from the TB clinic (at MMRC Xpert MTB/RIF testing is performed at the site), and self-reported HIV status will be assessed. 2 separate sputum samples will be obtained and stored (frozen) for later comparison to

recurrent isolates by WGS at OSR, Italy. During the 5-month period between V1 and V2, the study staff will regularly liaise with screened participants, staff from the TB clinics and community health care workers to monitor TB treatment compliance and continued eligibility for study participation.

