There will be short-term follow-up visits after each vaccination on V4= Day 14 and V6= Day 70, with weight, vital signs, TB symptoms screen and review of diary cards. Solicited AEs including injection site reactions and concomitant medications (CM), and spontaneously reported AEs, including serious AEs and AEs of special interest, will be assessed and recorded. If there is suspicion of TB disease, 2 separate sputum samples will be obtained, and the case verification procedure (see details below) for recurrent TB disease will be initiated.

For the safety cohort (= the first 150 randomized participants across all sites), see Table 2-1, there will also be safety laboratory testing on V4= Day 14 and V6= Day 70. For the remaining participants, there will only be laboratory safety testing at screening (V2), or at the ET Visit, if within 14 days after the investigational medicinal product (IMP) administration.

At the long-term follow-up visit on V7= Day 238, there will be a TB symptoms screen including weight and recording of serious adverse events (SAEs) and AEs of special interest. If there is suspicion of TB disease, 2 separate sputum samples will be obtained, and the case verification procedure (see details below) for recurrent TB disease will be initiated.

At the last study visit, V8= Day 421, whether or not there is suspicion of TB disease, 2 separate sputum samples will be obtained from all participants to identify missed cases, see Section 3.6.1. At this visit a negative Xpert MTB/RIF Ultra does not need to be verified by culture for participants with no clinical TB symptoms. Furthermore, SAEs and AEs of special interest will be assessed and recorded, if any.

Immunogenicity / immunology laboratory samples: PBMCs and plasma for ICS and IgG ELISA will be collected from all participants on V3= Day 0, V6= Day 70 and at suspicion of TB recurrence, as defined for the STB Visit, ET Visit or V8. Whole blood for RNA analysis and blood subset counts (to support the RNA analysis) will be collected from all participants at V3= Day 0 and at suspicion of TB recurrence, as defined for the STB Visit, ET Visit or V8, see Table 3-2.

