7.4.8 Clinical Laboratory and Vital Sign Parameters

For each clinical laboratory and vital sign parameter pre-specified in the protocol, summary statistics for continuous parameters will be presented by treatment group for all pre- and post-

vaccination assessments and for change from pre-vaccination to post-vaccination assessments.

The number (percentage) of participants with post-vaccination clinical laboratory values or vital sign values recorded as newly abnormal following study vaccination will be tabulated at each post-vaccination time point and overall. Clinical laboratory and vital sign abnormalities will also be reported as adverse events and included in the summaries of adverse events.

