2.2 Trial Design

A-055 is a phase 2, double-blind, randomised, placebo-controlled trial. In total 900 participants are planned to be randomised 1:1 to one of the following treatment groups:

- H56:IC31
- Placebo

There are two sub-cohorts in the trial.

- The first 150 randomised participants are planned to be included in the Safety cohort subgroup.
- The first 100 randomised participants at the [REDACTED] and [REDACTED] sites are planned to be included in the Immunogenicity cohort subgroup, 50 participants from each site.

The safety cohort will be used to evaluate safety at the following planned timepoints:

- After 150 participants across all sites have received the 1st vaccination and 14 days of safety data following the 1st vaccination is available
- After all participants in the safety cohort have received the 2nd vaccination and 14 days of safety data following the 2nd vaccination is available, except for participants withdrawn before this timepoint.

Presentations of data solely linked to the interim safety cohort reviews are not covered by this SAP.

The immunogenicity cohort will be used for evaluation of the immunogenicity of the H56:IC31 vaccine by WB ICS and IgG ELISA of plasma measured at baseline, and 14 days after the 2nd vaccination.

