4.1 Statistical Considerations

Baseline is defined as the last assessment with available data prior to the first vaccination. No statistical tests comparing treatment groups at baseline will be performed.

Categorical data will be summarised by treatment group, using number and percentages of participants. Continuous data will be presented using the number of participants (N), mean, standard deviation (SD), median, lower quartile, upper quartile, minimum and maximum. Both the absolute values and the change from baseline will be presented, if applicable. For calculation of percentages the denominator will be the number of participants in the analysis set, unless otherwise specified.

Descriptive statistics for all endpoints will be presented by treatment group and Visit (if applicable) using observed cases, i.e., no imputation of missing data will be performed. Missing data for time to event endpoints is handled using censoring.

All presentations will at least be by treatment group.

For summaries presented by visit, scheduled time will be used, and trial visits will be labeled as below:

Visit	Label
3	Visit 3 (Day 0) - Baseline
4	Visit 4 (Day 14)
5	Visit 5 (Day 56)
6	Visit 6 (Day 70)
7	Visit 7 (Day 238)
8	Visit 8 (Day 421)

The following labels will be used in tables, figures, and listings:

Treatment	Label
H56:IC31: 5 µg H56/500 nmol IC31	H56:IC31
Placebo	Placebo

All will be presented in UK English.

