Table 14.3.5.11: Hematology – Lymphocytes ($10^9/\text{L}$) by visit – Safety analysis set

<Layout similar to table 14.3.5.1>

Table 14.3.5.12: Hematology – Monocytes ($10^9/\text{L}$) by visit – Safety analysis set

<Layout similar to table 14.3.5.1>

Table 14.3.5.13: Hematology – Neutrophils ($10^9/\text{L}$) by visit – Safety analysis set

<Layout similar to table 14.3.5.1>

Table 14.3.5.14: Hematology – Basophils ($10^9/\text{L}$) by visit – Safety analysis set

<Layout similar to table 14.3.5.1>

Table 14.3.5.15: Hematology – Eosinophils ($10^9/\text{L}$) by visit – Safety analysis set

<Layout similar to table 14.3.5.1>

Table 14.3.5.16: Hematology – Platelets ($10^9/\text{L}$) by visit – Safety analysis set

<Layout similar to table 14.3.5.1>

Table 14.3.5.17: Urinalysis – Protein by visit – Safety analysis set

	H56:IC31 N (%)	Placebo N (%)
Safety analysis set (N)	xx	xx
Protein		
Visit 2 - Screening		
None	xx (xx.x)	xx (xx.x)
Trace	xx (xx.x)	xx (xx.x)
1+	xx (xx.x)	xx (xx.x)
2+	xx (xx.x)	xx (xx.x)
3+	xx (xx.x)	xx (xx.x)
>=4+	xx (xx.x)	xx (xx.x)
Positive	xx (xx.x)	xx (xx.x)
Negative	xx (xx.x)	xx (xx.x)
Small	xx (xx.x)	xx (xx.x)
Moderate	xx (xx.x)	xx (xx.x)
Large	xx (xx.x)	xx (xx.x)
20 mg/dL	xx (xx.x)	xx (xx.x)
30 mg/dL	xx (xx.x)	xx (xx.x)
100 mg/dL	xx (xx.x)	xx (xx.x)
500 mg/dL	xx (xx.x)	xx (xx.x)
Not Done	xx (xx.x)	xx (xx.x)
Total	xxx (xxx)	xxx (xxx)
Visit 4 (Day 14)		
None	xx (xx.x)	xx (xx.x)
Trace	xx (xx.x)	xx (xx.x)
1+	xx (xx.x)	xx (xx.x)
...		
Visit 6 (Day 70)		
None	xx (xx.x)	xx (xx.x)
Trace	xx (xx.x)	xx (xx.x)
1+	xx (xx.x)	xx (xx.x)
...		
Early termination visit		
None	xx (xx.x)	xx (xx.x)
Trace	xx (xx.x)	xx (xx.x)
1+	xx (xx.x)	xx (xx.x)
...		

Page 1 of 1

N: Number of participants, %: Percentages of participants
 Trial: <Trial id>
 Program: <program_name>.sas - output: <output_name>.rtf - executed: DDMMYYYY

Sponsor: SSI & IAVI Vaccine: H56:IC31 Trial: POR A-055	Document type: Table shells	Status: Final Version: 2.0 Date: 15 SEP 2023	
--	--------------------------------	--	--

Table 14.3.5.18: Urinalysis – Glucose by visit – Safety analysis set

<Layout similar to table 14.3.5.17>

Table 14.3.5.19: Urinalysis – Leukocytes by visit – Safety analysis set

<Layout similar to table 14.3.5.17>

Table 14.3.5.20: Urinalysis – Erythrocytes by visit – Safety analysis set

<Layout similar to table 14.3.5.17>

Sponsor: SSI & IAVI
Vaccine: H56:IC31
Trial: POR A-055

Document type:
Listing shells

Status: Final
Version: 2.0
Date: 15 SEP 2023

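### The laboratory tables omit the protocol's change and newly abnormal summaries, set about 450 per arm at Visit 2 beside about 75 at Visits 4 and 6, and leave the urinalysis denominator unsettled

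*SAP*

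**What the plan says.** On who is sampled, SAP section 7.2.3 states that the laboratory parameters "are measured at 2nd screening visit (Visit 2) for all participants, and at Visit 4 (day 14), Visit 6 (day 70"), and assigns the Visit 4 (V4), Visit 6 (V6) and early-termination (ET) measurements to the safety cohort. An ET sample is also taken from anyone whose ET visit falls within 14 days after dosing. Protocol section 2.2 agrees: "For the remaining participants, there will only be laboratory safety testing at screening (V2"), or at such an ET visit.

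On numbers, SAP section 2.2 gives the planned sizes: "In total 900 participants are planned to be randomised 1:1" and "The first 150 randomised participants are planned to be included in the Safety cohort subgroup". Protocol Table 2-1 splits the row "First 150 randomized participants across all sites Safety cohort subgroup" into 75 and 75.

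On presentation, SAP section 7.2.3 asks for biochemistry and haematology by visit and treatment in tables and boxplots, urinalysis by the recorded categories, and a listing of out-of-range values. All twenty shells, 14.3.5.1 to 14.3.5.20, use the safety analysis set, which is everyone who received at least one dose. Shell 14.3.5.17, for example, is headed "Urinalysis – Protein by visit – Safety analysis set". The rows are Visit 2 (V2), V4, V6 and ET. No shell has a row for change or for newly abnormal values.

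On the governing rules, SAP section 4.1 says "For calculation of percentages the denominator will be the number of participants in the analysis set, unless otherwise specified". The same section has change from baseline shown where applicable. Protocol section 7.4.8 requires summary statistics for each laboratory parameter at all pre- and post-vaccination assessments "and for change from pre-vaccination to post-vaccination assessments". It also requires the number and percentage of participants newly abnormal at each post-vaccination time point and overall. SAP section 9, which lists departures from the protocol's analyses, mentions neither item.

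**The concern.** A table stacked by visit invites the reader to go from the V2 row to the V4 and V6 rows and take the difference as what happened after vaccination. Here those rows describe different groups. V2 holds everyone; V4 and V6 hold the first 150 randomised. That cohort is not a random sample over calendar time, and protocol amendment 4 later let participants enter through a combined screening visit. Any difference in enrolment period or site mix would therefore appear as a laboratory shift.

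Treatment status also changes between the rows. V2 falls at or after week 22 of TB treatment, and treatment may not run beyond 28 weeks. V6 is scheduled 10 weeks after the first vaccination, so at week 22 + 10 = 32 or later, when treatment has ended. Within-person change, compared between arms, is the summary that deals with both problems. It is also the one the protocol asks for and the shells lack.

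A second issue is the urinalysis percentages. Under the general denominator rule, a finding that is common among those tested could be printed as rare.

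**Working it through.** The plan contains no computed laboratory figure to reproduce. The inputs are the planned counts, which agree with each other: 450 + 450 = 900 randomised (SAP section 2.2, Protocol Table 2-1) and 75 + 75 = 150 in the safety cohort. The safety analysis set is taken as about 900, assuming nearly all randomised participants receive a dose.

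**1. Share of V2 with no scheduled follow-up sample.** (900 − 150)/900 = 750/900 = 83.3%. Per arm, (450 − 75)/450 = 375/450 = 83.3%.

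**2. Effect on the before-after reading.** In one arm, let the cohort's V2 mean be m, the V2 mean of the other 375 be m + d, and the cohort's true mean change to V4 be c.
- Displayed V2 mean: [75m + 375(m + d)]/450 = m + 0.833d.
- Displayed V4 mean: m + c.
- Displayed shift: c − 0.833d.

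The documents give no value for d, so the size of this error is unknown, and it is zero if d = 0. If d is the same in both arms, as randomisation would lead one to expect, it cancels when the two arms' shifts are compared.

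**3. Urinalysis denominator at V4 and V6 (Tables 14.3.5.17 to 14.3.5.20).**
- Ratio of the default denominator to the number scheduled for testing: 450/75 = 6.
- Illustration: 15 of 75 tested is 20%; divided by 450 it is 3.3%.
- All result categories together could reach at most 75/450 = 16.7%.
- If only 90% to 95% of the cohort is sampled (an assumption), the factor is 450/67.5 = 6.7 to 450/71.25 = 6.3.
- At V2 everyone is tested, so the factor is 450/450 = 1.
- Between arms, (a/450)/(b/450) = a/b = (a/75)/(b/75), so the ratio is unchanged. A difference in percentage points would shrink by the same factor of 6.

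**4. Required against planned.** Protocol section 7.4.8 asks for three things: values, change, and newly abnormal counts. SAP section 7.2.3 and the laboratory shells supply only the first. SAP section 4.1 defines baseline as the last available assessment before first vaccination, so for scheduled laboratory data baseline is V2 and change can be computed in the cohort. Elsewhere the SAP is explicit when change is wanted: section 7.2.2 specifies it for vital signs and weight, and weight has its own change table (14.3.3.6).

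**The case against.** The strongest reply is that the comparison the trial exists to make is sound. The objective is safety against placebo, and at V4 and V6 the tables set about 75 against about 75 randomised participants from the same cohort. A reader might infer from the mixed populations that the arm comparison is biased. The documents do not support that: the sampling rule is the same in both arms, and any dilution of percentages is too.

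The change in population is also not hidden. SAP section 7.2.3 says who is sampled, and the continuous shells print N at each visit. This stands, but a visible N does not turn an unpaired reading into a paired one.

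A reader might also infer that the urinalysis percentages will certainly be six times too low. That goes too far. SAP section 4.1 allows exceptions to its rule and says descriptive statistics use observed cases. Shell 14.3.5.17 has a Not Done category and a Total row at each visit, which may signal a per-visit denominator. If untested people were counted as Not Done, that row would show about 375/450 = 83.3% and the dilution would be plain on the page. What remains is a stated default that gives the wrong answer if followed, and no text in section 7.2.3 or the shell that overrides it.

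Finally, laboratory parameters are additional safety assessments in SAP section 7.1, individual values and clinically significant results are listed, and protocol section 7.4.8 says abnormalities are also reported as adverse events. This lowers the stakes. It does not replace the missing tabulations: listings give no rates by arm, and protocol section 3.6.3.2 leaves reporting a laboratory change as an adverse event to the investigator's discretion.

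**Conclusion.** The point holds in limited form, and the tables should be corrected. Two laboratory summaries required by protocol section 7.4.8, change and newly abnormal counts, are absent from SAP section 7.2.3 and its shells and are not declared in section 9. It would be too strong to say that the SAP drops change altogether, because section 4.1 still promises it where applicable; the documents conflict on this and need to be reconciled.

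The V2 to V4/V6 reading rests on different people. About 83% of V2 contributors have no scheduled post-vaccination value, and the displayed shift is off by 0.83d for an unknown d. The urinalysis understatement is conditional: about 6-fold, at V4 and V6, in four of the twenty tables, in both arms, and only if the section 4.1 default is applied. V2 percentages are unaffected, and so is the between-arm ratio at each visit. These figures assume the planned counts of 450 and 75 per arm.

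**What to change.** Keep Tables 14.3.5.1 to 14.3.5.20 on the safety analysis set. Restricting them all to the safety cohort is tempting, but it would drop the ET results that protocol section 2.2 requires from participants outside the cohort. Then:

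- Add, for safety-cohort participants with a V2 value, the V2 values and the change from V2 to V4 and from V2 to V6, by arm.
- Add the number and percentage newly abnormal at each post-vaccination time point and overall, by arm, with a definition of newly abnormal relative to V2.
- State in SAP section 7.2.3 that percentages for urinalysis and for newly abnormal values use participants with a result at that visit as the denominator. For the overall row, use those with at least one post-vaccination result.
- If either protocol summary is deliberately left out, declare it in SAP section 9 with the reason.

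The cost is a few sentences in section 7.2.3 and edits to the shells; no new data are needed. The same edit can remove a duplicate, since shells 14.3.5.2 and 14.3.5.4 are both ALT.
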